15.7. Secondary and Exploratory Endpoint Analysis

Secondary and exploratory endpoints based on *patient-level* data will be analyzed using similar methods to the primary and key secondary endpoints, using Wilson (score) confidence intervals. Re-operation rates will be compared between treatments using Fisher's exact tests.

Secondary and exploratory endpoints based on *orientation-level, primary specimen-level, and point-level* data will be analyzed using a weighted estimator, proposed by Lee and Dubin (Lee and Dubin, 1994), which takes into account the correlation (clustering) of the margins within a patient. This method will be used to calculate the estimates and two-sided 95% confidence intervals.

Descriptive statistics will be used to summarize the weight of resected tissue specimens (SoC specimens vs. FGR specimens). Mean total tissue weight (Arm 1 vs. Arm 2) will be compared using a two-sample t-test.

Breast-Q survey results will be summarized using actual values and change from baseline values using descriptive statistics. The difference in change scores between Arm 1 and Arm 2 will be summarized descriptively and presented along with a 95% confidence interval on the difference in means. For the Breast-Q survey results at 3 months, if the lower bound of this confidence interval is \geq - 10 then non-inferiority will be claimed. Results at 6 months and 1 year will be described with summary statistics. For the analysis of Breast-Q survey results, the previously defined minimal important difference as the reference point for what patients consider a meaningful change in Breast-Q scores. The minimal important difference is defined as: "The smallest difference in score in a domain of interest that patients perceive as beneficial and which would mandate, in the

|--|

absence of troublesome side effects and excessive cost, a change in the patient's (health care) management''⁷⁰. While patients in Arm 2 are anticipated to have marginally more tissue removed as a result of *FGR* as compared to SoC [analyzed in secondary endpoint P(2.16)], it is not anticipated that resection of this additional tissue will negatively affect the patient's satisfaction with the appearance of their breasts as compared to patients in Arm 1. For secondary endpoint 18 [P(2.18a) & P(2.18b)] we have defined a mean difference in change score \leq -10 (Arm 1 – Arm 2) as meeting our criterion for non-inferiority. Previous studies have reported a minimal important difference in Breast-Q scores of 7-8⁷¹ for the breast satisfaction subscale in breast reconstruction patients. To date there are no known publications addressing the minimal important difference using the Breast Conserving Therapy module of the Breast-Q survey. While a change score of \geq -10 would represent a negative change in breast satisfaction, this risk may still be considered acceptable to patients if the intervention is associated with improved clinical outcomes (e.g. decreased probability of having positive margins).

Depth of tumor analyses of tissue specimens identified by FL imaging will be summarized using descriptive statistics.

Exploratory subgroup analyses will be performed on key efficacy endpoints. Subgroups will include patients who underwent sentinel node mapping with blue dye injection vs. those who did not, and patients who underwent comprehensive circumferential shaves during surgery vs. those who had selective shaves during BCS.

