Only data from participants in Part B will be used for the analyses of primary and secondary efficacy. Data from all participants in both Part A and Part B will be used for the evaluation of safety.

In Part B of the study, participants will be randomized in a ratio of 1:6 (Arm 1 [SoC]: Arm 2 [PD G 506 A]).

The randomization will be stratified by breast cancer type (invasive carcinoma with or without in situ carcinoma vs. in situ carcinoma alone). This will ensure an approximate ratio of 1:6 within each type of breast cancer. Preoperative diagnosis based on diagnostic tissue sampling performed during screening (e.g. percutaneous core needle biopsy, fine-needle aspiration cytology) will be

SBI-CIP 20-002 Rev: v1.8 A prospective multi-center clinical study evaluating the use of PD G 506 A and the Eagle V1.2 Imaging System for the visualization of carcinoma during breast conserving surgery	Page: 46 of 157
---	-----------------

used for stratification. Permuted blocks will be used to construct the randomization schedule and the randomization will be implemented using an interactive web response system.

Data from the SoC arm (Arm 1) will not be used for statistical analysis of the primary and most secondary endpoints. The purpose of the SoC arm is to compare resected tissue weight, patient reported cosmetic outcomes, re-excision prior to initiation of adjuvant therapies, re-excision within 1-year of index BCS, and safety between study arms as well as to minimize bias introduced into the SoC procedure if the *surgeon* is aware that they have an opportunity to revise the margins further after SoC is complete. A 3-month, 6-month and 1-year follow-up will be performed to evaluate patient reported cosmetic outcomes as well as the rate of re-excision across both study arms. The 6-month and 1-year follow-up data will be collected as an extension phase to the study, meaning database lock and analysis of all other endpoints will be performed following the last patient's 3-month follow-up data is collected. Analysis of 6-month and 1-year data will occur after the last patients 1-year visit. The clinical study report will be appended to include the 6-month and 1-year data, when available.

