15.1. General Considerations

Descriptive summaries of variables will be provided where appropriate. For continuous variables, the number of non-missing values (n) and the median, mean, standard deviation, minimum, and maximum will be tabulated. For categorical variables, the counts and proportions of each value will be tabulated. Confidence intervals will also be provided as appropriate. All statistical tests will be performed at the 0.05 level.

Further details on all analyses will be provided in the statistical analysis plan (SAP).

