15.2. Sample Size Estimation

The sample size of Part A has been chosen on pragmatic grounds to be approximately 75 study patients. The number of patients ultimately included in Part A will be decided by the Steering Committee and the Sponsor based on the perceived understanding of the protocol by clinical sites and the feedback obtained during the Part A training phase. Part A will not be randomized; all study patients in Part A will receive PD G 506 A. Data acquired from Part A will be used to confirm the Investigators' understanding of fluorescence guided resection (FGR) procedures in the protocol and to confirm the sample size for Part B. Only data from participants in Part B will be used for the analyses of primary and secondary efficacy. Data from all patients in both Part A and Part B will be used for the evaluation of safety and analyses will include assessments of data from Part A and Part B separately, as well as all study patients (Part A and Part B together).

P(1.1) Conversion Rate among all patients =

patients with at least one histopathology-positive margin following SoC and histopathology negative final margins after FGR

All patients imaged (Arm 2)

SBI-CIP 20-002 Rev: v1.8 A prospective multi-center clinical study evaluating the use of PD G 506 A and the Eagle V1.2 Imaging System for the visualization of carcinoma during breast conserving surgery	Page: 96 of 157
---	-----------------

The sample size in Part B of the study is only driven by the primary endpoint P(1.1). The primary endpoint is intended to determine the percentage of patients with at least one histopathology-positive margin after SoC who then have all histopathology-negative margins after FGR (conversion rate among all patients in Arm 2). To demonstrate benefit, the point estimate P(1.1) must be statistically significantly greater than 1%. By meeting this primary endpoint, we will demonstrate that FGR adds clinical benefit above and beyond what is achieved with SoC.

Based on the expected 3% conversion rate estimate for P(1.1), a total of 500 patients will be required in Part B of the study to demonstrate statistical significance at a Type 1 error level of 0.05 with 90% power using a 2-sided Z test for a binomial proportion assuming a null hypothesis proportion of 1%.

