Using a randomization ratio of 1:6 (Arm 1-SoC; Arm 2: PD G 506 A), a total sample size of 525 patients (Arm 1: N=72; Arm 2: N=428) would be required, accounting for a 5% loss to follow-up. The primary efficacy analysis will be based on the mITT (modified intention-to-treat population), which includes all Part B patients randomized to Arm 2 who undergo surgery and have recorded surgical histopathology data.

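### The between-arm re-operation and tissue-weight tests leave out the randomisation stratum; analysing by it, and replacing Fisher's exact test, is a small and cheap improvement

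*Combined protocol and SAP*

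**What the plan says.** Section 8.1 of the protocol sets the design: "The randomization will be stratified by breast cancer type (invasive carcinoma with or without in situ carcinoma vs. in situ carcinoma alone"). It gives the aim as balance within strata: "This will ensure an approximate ratio of 1:6 within each type of breast cancer".

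Section 15.7 gives the between-arm methods. For re-operation, endpoints P(2.15) and P(2.16): "Re-operation rates will be compared between treatments using Fisher's exact tests". For tissue weight: "Mean total tissue weight (Arm 1 vs. Arm 2) will be compared using a two-sample t-test". Neither test is described as stratified or adjusted. Section 15.7 names no between-arm difference with a confidence interval for re-operation, and cancer type is not among its listed subgroups. Section 15.1 adds that "All statistical tests will be performed at the 0.05 level" and leaves further analysis detail to a SAP, whose text is not in the combined document as supplied.

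Section 15.2 gives the size of the comparison: "Arm 1: N=72; Arm 2: N=428) would be required, accounting for a 5% loss to follow-up". It also says that the primary endpoint alone drives the sample size. Section 15.6 says that only the primary endpoint must be significant for a positive study.

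**The concern.** When randomisation is stratified, between-stratum variation is balanced across the arms by design. A test that ignores the stratum still counts that variation as noise, so it is somewhat conservative if the factor is prognostic. Cancer type is plausibly prognostic for re-operation: the protocol follows separate margin guidelines for invasive disease and DCIS, and P(2.16) counts re-operations due to positive final margins. Fisher's exact test adds conservatism of its own, because it conditions on the margins of a discrete table.

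These comparisons matter to the design. Section 8.1 says that Arm 1 exists largely to compare tissue weight, cosmetic outcome, re-excision and safety. With only 72 controls, precision that can be had for a change of wording is worth having.

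**Working it through.** **Inputs from the protocol.** Arm sizes 72 and 428, and alpha 0.05 (Sections 15.1, 15.2); expected conversion of 3% among all Arm 2 patients (Section 15.2) and above 15% among SoC margin-positive patients (Section 15.6.2); background re-excision rate 23% (Section 6.1.1).

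**Assumptions, not in the protocol.** The in situ share, the re-operation rates by cancer type, the size of any reduction in re-operation, and the variance in tissue weight explained by cancer type.

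**Step 1. The plan's own figure.** For a one-sample z test, n = [(z₀.₉₇₅√(p₀q₀) + z₀.₉₀√(p₁q₁))/(p₁ − p₀)]². With p₀ = 0.01 and p₁ = 0.03, n = [(1.960 × 0.0995 + 1.282 × 0.1706)/0.02]² = 427.7, so 428 in Arm 2. Then 428 × 7/6 = 499.3, about 500, and 500 × 1.05 = 525. The figure reproduces. Since 72 + 428 = 500, the printed arm sizes are those before inflation for loss. No power is stated for re-operation or tissue weight.

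**Step 2. Size and power without strata.** Exact enumeration of two-sided tests, 72 vs 428:

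| Arm 1 vs Arm 2 rate | Fisher | Chi-square |
|---|---|---|
| 10% vs 10% (size) | 3.9% | 4.8% |
| 20% vs 20% (size) | 4.2% | 4.9% |
| 23% vs 20% | 8.6% | 9.8% |
| 23% vs 11.5% | 68.7% | 72.4% |

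Fisher costs 1.2 points for the small effect and 3.7 points for the halving.

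**Step 3. What stratifying adds.** CMH statistic: with a_k events among n₁k controls and n₂k Arm 2 patients in stratum k, m_k events in total and N_k patients, X² = (Σ(a_k − n₁k·m_k/N_k))² / Σ[n₁k·n₂k·m_k(N_k − m_k)/(N_k²(N_k − 1))]. Simulation with 40,000 runs, 20% in situ alone and re-operation halved. Both rate pairs average 20% in Arm 1: 0.8 × 16 + 0.2 × 36 = 20, and 0.8 × 15 + 0.2 × 40 = 20.

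| Arm 1 rates, invasive/in situ | Fisher | Chi-square | CMH, uncorrected | CMH, continuity-corrected |
|---|---|---|---|---|
| 16%/36% | 60.9% | 65.3% | 66.6% | 60.1% |
| 15%/40% | 60.7% | 65.4% | 67.2% | 60.5% |
| Size under the null | 3.6-3.8% | 4.3-4.6% | 5.0-5.1% | 3.4% |

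Of the total gains of 5.7 and 6.5 points, dropping Fisher for chi-square gives 4.4 and 4.7; stratifying gives 1.3 and 1.8. These pairs assume strong risk ratios between strata (36/16 = 2.25; 40/15 = 2.67). With ratios of 1 to 2 and an in situ share of 15-25%, CMH stays within 0.7 points of chi-square, sometimes just below it. A continuity correction removes the whole gain.

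**Step 4. An effect nearer the plan's expectations.** If each conversion avoids one re-operation, 23% falls to 20%, a relative risk of 20/23 = 0.87. Conversion of 15% of SoC-positive patients gives 1 − 0.15 = 0.85. At 0.87 with strata, power is 7.9-8.4% for Fisher and 9.4-10.1% for CMH with risk ratios of 1 to 2. In the Step 3 scenarios it is 7.2% vs 9.5% and 6.7% vs 9.4%.

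The Arm 1 size needed for 80% power at 23% vs 20% and 1:6 follows from n₁ = [z₀.₉₇₅√(p̄q̄ × 7/6) + z₀.₈₀√(p₁q₁ + p₂q₂/6)]²/(p₁ − p₂)². With p̄ = (0.23 + 6 × 0.20)/7 = 0.2043, n₁ = 1,691. The trial has 72.

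**Step 5. Tissue weight.** The standard error in SD units is √(1/72 + 1/428) = 0.127. For a standardised difference of 0.3 (assumed), power is Φ(0.3/0.127 − 1.96) = 65.4%. If cancer type explains a share R² of the variance, the standardised difference becomes 0.3/√(1 − R²), and power is 65.8%, 67.6% and 69.9% for R² of 1%, 5% and 10%: gains of 0.4, 2.2 and 4.5 points.

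**The case against.** The strongest case for leaving the plan alone has four parts.

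- **Fisher buys something.** It guarantees size at or below 5%, whereas CMH is asymptotic. If the in situ share is 20%, that stratum holds about 72 × 0.20 = 14 controls, so choosing an exact test is defensible. A reader might infer that Fisher loses power for no benefit and that changing it has no downside; this guarantee shows otherwise.
- **The attractive power figures rest on a halving of re-operation.** A reader might take that as the planned effect, but it is not in the protocol. The plan's conversion figures point to a relative risk near 0.85-0.87, where no choice of test makes the comparison informative.
- **Fisher's conservatism says nothing about tissue weight**, which is compared by a t-test. The loss there turns on a variance share that the protocol does not give.
- **The stakes are low.** The primary analysis does not use Arm 1, neither comparison has stated power or decides success, and the SAP may yet add adjustment.

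All four stand as limits on size. They do not remove the point: Section 15.7 states these methods outright, the stratum is known for every randomised patient, and keeping Fisher as a sensitivity analysis retains its protection. Deferral to the SAP makes the SAP the natural place for the change.

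**Conclusion.** The point holds as a minor improvement. The named between-arm tests do not reflect the stratified randomisation, and Fisher runs at about 3.6-4.3% actual size. For an assumed halving of re-operation, moving from Fisher to uncorrected CMH raises power from about 61% to 66-67% in the Step 3 scenarios, with 0-2 points due to stratifying, depending on how prognostic cancer type is. For tissue weight the gain is 0.4-4.5 points under the Step 5 assumptions.

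It would go too far to infer that the planned tests are invalid or inflate false positives: the re-operation test errs on the conservative side. Nor would the change rescue the re-operation comparison. Near a relative risk of 0.87, power stays at about 7-10% whichever test is used, because Arm 1 is small. The stratum inputs are all assumed; separate margin guidelines make a prognostic effect plausible but do not measure it.

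**What to change.** Before the between-arm data are unblinded for analysis, write into the SAP:

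- **P(2.15) and P(2.16):** a CMH test stratified by cancer type as randomised, explicitly without continuity correction, with a stratified risk difference and its 95% confidence interval. Keep Fisher's exact test as a sensitivity analysis.
- **Total tissue weight, Arm 1 vs Arm 2:** a linear model with arm and cancer type in place of the unadjusted t-test, reporting the adjusted difference and 95% confidence interval.

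The cost is wording and programming only, with no new data or patients. The one small loss is the exact size guarantee in the main re-operation test, which the sensitivity analysis covers. The report should also say that the re-operation comparison has little power for modest effects, and should lead with the interval rather than the p-value.

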following index BCS (Arm 1 and Arm 2).	suspected residual disease (patient-level analysis; Arm 1 and Arm 2).	# of patients in Arm 1 that underwent a 2 nd surgery on the ipsilateral breast within 1 year of index BCS # of patients in Arm 1 # of patients in Arm 2 that underwent a 2 nd surgery on the ipsilateral breast within 1 year of index BCS # of patients in Arm 2	x100%	
16. To characterize the impact of FGR on the rate of 2 nd surgery shortly after index BCS (Arm 1 and Arm 2).	Percentage of patients receiving an early 2 nd surgery (planned or actual) on the ipsilateral breast related to positive final margins prior to radiation or medical management (patient-level analysis; Arm 1 and Arm 2).	# of patients in Arm 1 that underwent or are scheduled to undergo a 2 nd surgery on the ipsilateral breast due to positive SoC final margins following initial BCS prior to radiation or medical management # of patients in Arm 1	x100%	Patient-level early reoperation rate.
		P(2.16b) Arm 2 only = # of patients in Arm 2 that underwent or are scheduled to undergo a 2 nd surgery on the ipsilateral breast due to positive FGR final margins following initial BCS prior to radiation or medical management # of patients in Arm 2	x100%	

SBI-CIP 20-002 Rev: v1.8 A prospective multi-center clinical study evaluating the use of PD G 506 A and the Eagle V1.2 Imaging System for the visualization of carcinoma during breast conserving surgery Page: 38 of 157	·
--	---

Secondary Objectives	Parameter Description	Parameter Formula	Abbreviated Description
17. To characterize the impact	Sum of the weight (mg) of all tissue	P(2.17a) =	Amount of tissue removed
of FGR during BCS on the	removed based on SoC compared to the	Mean SoC tissue weight (mg) Arm 1 and Arm	with FGR beyond SoC.
amount of tissue removed	sum of the weight (mg) of all tissue	2:	
(Arm 1 and Arm 2).	removed based on FGR (patient-level	SoC tissue weight = Primary specimen (mg) +	
	analysis; Arm 1 and Arm 2).	SoC-driven cavity shave specimen(s) (mg)	
		P(2.17b) =	
		Mean FGR tissue weight (mg) Arm 2 only:	
		Total tissue weight = FL-driven cavity shave	
		specimen(s) (mg)	
18.To characterize the impact	Patient satisfaction with the cosmetic	P(2.18a) =	Patient satisfaction.
of FGR during BCS on the	outcome of breast conserving surgery	Mean Breast-Q Breast Conserving Therapy	
patient-reported cosmetic	performed based on SoC in	Module satisfaction with breasts score before	

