8.3. Minimizing Bias

The following precautions are in place to minimize bias in data collection:

- No personnel involved with the surgical procedure (i.e., *surgeon*, *surgeon's assistant*) will be aware of the participant's randomized treatment assignment nor be present when the participant is provided with the study drug to ingest.
 - o Blinded research personnel will be instructed not to solicit any information from the participant regarding the taste and/or smell of the investigational drug.
- The participant will be blinded to whether they have been randomized to Arm 1 or Arm 2 for the duration of the study.
- The *surgeon* will be blinded to whether a participant has been randomized to Arm 1 or Arm 2 until the time at which the *surgeon* declares the SoC lumpectomy is complete.
- The individual (e.g. pathologist's assistant, pathologist) processing the surgical specimen(s) will be blind to the manner (e.g. SoC vs. *FGR*) by which samples are obtained and the FL status of the samples. This individual will also be blind to the fluorescence

SBI-CIP 20-002 Rev: v1.8 A prospective multi-center clinical study evaluating the use of PD G 506 A and the Eagle V1.2 Imaging System for the visualization of carcinoma during breast conserving surgery	Page: 47 of 157
---	-----------------

- imaging data collected of the bisected/serially sectioned primary specimen during the perioperative procedures.
- The pathologist performing the histopathological evaluation will be blind to the manner (e.g. SoC vs. *FGR*) by which the samples are obtained and the FL status of the samples.
- To ensure FL-imaging does not influence **SoC margin assessment**, intraoperative data collection tools will document the completion of SoC prior to the **surgeon** being given access to any previously acquired FL imaging data and performing additional FL imaging.

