12.4.4.2. Specimen Grossing

All specimens (excluding biopsies taken from the *primary specimen*) will be individually weighed prior to fixation in formalin, and the mass (mg) will be recorded on the Pathology Data Collection Tool.

Specimen grossing and fixation will be performed as per SoC, including inking of all surfaces of the *primary specimen* and both the inside and outside surface of all *cavity shave specimens*. To adjudicate the *orientation-level* endpoints, the inside and outside surfaces of all *cavity shave specimens* must be inked with different colors (visually obvious) of ink. The *primary specimen* and any *cavity shave specimens* will be submerged in formalin within the site-mandated time post-resection (i.e. ischemic time).

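### The only test of tissue weight compares whole-resection totals in 72 versus 428 patients, so it has under 50% power for an increment below about 0.25 SD, while the directly weighed FGR increment has no committed confidence interval

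*Combined protocol and SAP*

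**What the plan says.** Objective 17 in Section 7.2.2 asks how much tissue FGR removes beyond SoC. P(2.17a) is the mean SoC weight (primary specimen plus SoC-driven shaves) in both arms. P(2.17b) is "Mean FGR tissue weight (mg) Arm 2 only", computed from the FL-driven shaves. The formula under P(2.17b) labels those shaves alone as the total tissue weight, and it does not say whether an Arm 2 patient with no shave counts as zero.

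Section 12.4.4.2 says that specimens other than biopsies "will be individually weighed prior to fixation in formalin, and the mass (mg) will be recorded on the Pathology Data Collection Tool". The SoC and FL-driven parts are therefore known separately for each patient.

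Section 8.3 keeps the surgeon unaware of the allocation until SoC resection has been declared finished. The SoC weight is thus settled before the allocation is revealed.

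Section 15.7 summarises SoC and FGR specimen weights descriptively and then plans one test: "Mean total tissue weight (Arm 1 vs. Arm 2) will be compared using a two-sample t-test". It also states that "patients in Arm 2 are anticipated to have marginally more tissue removed", but gives no figure. Section 15.1 promises confidence intervals only where appropriate.

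Section 15.2 sizes Part B on P(1.1) alone. Section 8.1 lists comparison of resected tissue weight among the purposes of the SoC arm.

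**The concern.** Total weight is SoC weight plus FL-driven weight. The first part varies with lumpectomy size, which FGR does not influence. The second part is the quantity of interest and is zero throughout Arm 1. A comparison of totals therefore estimates the increment plus the chance difference in SoC weight between the arms, and that chance difference is governed mainly by the 72 patients in Arm 1.

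If the increment is small relative to the spread of whole-resection weights, the test will often be non-significant. A reader could take that as evidence that FGR removes no additional tissue, although the separately weighed shaves of the same patients measure the addition directly. The amount of extra tissue is relevant background to the expectation in Sections 6.2.6 and 15.7 that cosmetic outcome will not suffer.

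**Working it through.** **Inputs from the documents.** Arm sizes 72 and 428 and the 0.05 level (Sections 15.1 and 15.2; two-sided is assumed for this test). Expected 3% conversion among all patients (15.2), more than 15% among SoC-positive patients, specificity above 80% and sensitivity above 70% (15.6.2).

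**The plan's own sample size.** n = [(1.96 × √(0.01 × 0.99) + 1.2816 × √(0.03 × 0.97)) / 0.02]² = 427.7, so 428 in Arm 2; 428 × 7/6 = 499, about 500. The stated figure is reproduced. It says nothing about tissue weight, for which no power is given.

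**Power of the t-test, in SD units of total weight.** The standard error of the difference is √(1/72 + 1/428) = 0.1274 SD.
- 50% power: 1.96 × 0.1274 = 0.25 SD
- 80% power: (1.96 + 0.8416) × 0.1274 = 0.357 SD
- 90% power: (1.96 + 1.2816) × 0.1274 = 0.413 SD

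| True increment (SD) | 0.05 | 0.10 | 0.15 | 0.20 | 0.25 | 0.30 | 0.40 |
|---|---|---|---|---|---|---|---|
| Power | 7% | 12% | 22% | 35% | 50% | 65% | 88% |

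The documents print 72 + 428 = 500 as the split of 525. With 75 versus 450 the 80% figure is 0.349 SD, essentially the same.

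**Share of Arm 2 likely to be shaved.** SoC-positive share 3%/15% = 20%. FL-positive share = 0.20 × 0.70 + 0.80 × 0.20 = 0.30. Varying the SoC-positive share over 15% to 25%, with sensitivity/specificity of 70/80, 50/70 or 70/90, gives 19% to 35%.

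**What a shave must weigh.** At 30%, shaves must average 0.25/0.30 = 0.83 SD of whole-resection weight for 50% power, and 0.357/0.30 = 1.19 SD for 80%. The documents give no SD. For an assumed coefficient of variation (CV) of 0.3, 0.5, 0.75 or 1.0, the 50% threshold is a shave weighing 25%, 42%, 62% or 83% of the mean SoC weight.

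**Illustration (assumed weights, in units of mean SoC weight).** Take whole-resection CV 0.5, shaves of 0.20 with CV 0.5, and 30% shaved.
- Mean increment: 0.30 × 0.20 = 0.06
- Variance of FL-driven weight: 0.30 × 0.04 × 1.25 − 0.06² = 0.0114
- Between-arm SE: √(0.25/72 + 0.2614/428) = 0.0639; half-width 12.5%; power about 15%
- Direct SE in Arm 2: √(0.0114/428) = 0.0052; half-width 1.0%

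The direct interval is about 12 times narrower. Over CV 0.3 to 1.0 and shaves of 10% to 50% of mean SoC weight, it is about 3 to 49 times narrower.

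**What adjustment does.** Write S for SoC weight, F for FL-driven weight and c for the fitted slope on S. Since F = 0 in Arm 1:
- unadjusted difference = mean F in Arm 2 + (mean S in Arm 2 − mean S in Arm 1)
- adjusted difference = mean F in Arm 2 + (1 − c) × (mean S in Arm 2 − mean S in Arm 1)

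With c near 1, the lumpectomy-size noise drops out and the estimate is close to P(2.17b). In simulations with skewed SoC weights (SD 20, 40 or 60 g), 30% shaved and mean shave weight 5, 10 or 20 g, all assumed, Welch power on totals was 7% to 61% with half-widths of 5 to 15 g. The adjusted half-widths were 0.26 to 1.02 g. For 10 g shaves the simple Arm 2 interval matches: SD of F = √(0.30 × 125 − 9) = 5.34 g, and 1.96 × 5.34/√428 = 0.51 g.

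**The case against.** The strongest reply is that nothing is lost. P(2.17b) is the increment, Section 15.7 summarises it, and a mean and SD give its precision. The adjusted model returns nearly the same number with nearly the same interval. This stands in large part: a reader might infer that the plan ignores the increment, and it does not. What remains is that no interval is committed, the handling of unshaved patients is unstated, and the only formal inference is on a noisier quantity.

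A second reply is that the t-test answers a legitimate randomised question, the net difference in tissue, including any change in SoC resection. SoC weight is measured after randomisation and dosing, and Sections 10.3 and 12.4.3 provide for accidental early unblinding. This also stands, and it is why the unadjusted contrast should be kept and SoC weight shown by arm.

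Third, a reader might infer that the test will probably miss a real increase. The documents do not support that without conditions, because they give neither an SD nor an increment. At CV 0.3 with shaves of 40% of mean SoC weight, power is 86%.

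Fourth, a reader might credit adjustment with near-100% power. That compares unlike things: FL-driven weight cannot be negative, so rejecting zero is almost automatic once shaves are taken. The gain is in precision only.

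Finally, study success rests on P(1.1), and the formal cosmetic criterion is Breast-Q non-inferiority. Neither depends on this test.

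**Conclusion.** The point holds in conditional form. The planned t-test has under 50% power for any increment below about 0.25 SD of total weight and needs about 0.36 SD for 80%; these figures rest only on the arm sizes and a two-sided 0.05 level. That the true increment lies in the low-power range is a judgement. It draws on the plan's expectation of a marginal increase and on an FL-positive share of about 30%, which is itself derived from expectations stated as lower bounds. The gram and CV figures are assumptions. A non-significant result would be uninformative about whether extra tissue was removed, and the plan should say so and lead with the more precise estimate. This is an inexpensive improvement to a secondary analysis, not a flaw in the primary conclusion.

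**What to change.** In Section 15.7 and the SAP, replace the t-test sentence with text to this effect:

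- Total tissue weight is the primary specimen plus SoC-driven shaves plus FL-driven shaves.
- The main estimate of tissue removed beyond SoC is the between-arm difference in total weight from a linear model with arm and SoC tissue weight, using HC3 standard errors, with its 95% CI.
- P(2.17b) is reported alongside with a 95% CI over all Arm 2 patients, counting zero where no shave was taken.
- SoC tissue weight is shown by arm with a CI for the difference.
- The unadjusted difference in total weight is kept, with its CI, as the randomised net comparison.
- Interpretation rests on the estimates and intervals. A non-significant difference is not evidence that no extra tissue was removed.

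At the same time, correct the label under P(2.17b) and the reference in Section 15.7 to P(2.16), which should be P(2.17).

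The cost is a few sentences and no new data, since every weight required is already collected. The small downside is that the adjusted estimate assumes SoC resection is unaffected by allocation; the SoC-weight comparison and the unadjusted contrast help to check this.
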